CECIDOC Study

Combination of ECG and Cardiovascular risk factors could Increase Diagnostic performance Of Chest pain triage at ED

Study Protocol and Statistical Analysis Plan 04-09-2019

[name], [name], [name], [name], [name], [name], [name], [name].

Université Catholique de Louvain

St Luc University Hospital

PI : [name]

[contact]

Background

Acute chest pain triage in the Emergency Department (ED) may prove challenging, since similar symptoms can reveal both mild or life-threatening disorders, and the clinical presentation itself is known not to be reliable for evaluating the risk of acute coronary syndrome (ACS)^{1,2}.

The first priority in patients with suspected ACS is to identify those with ST-elevation myocardial infarction (STEMI), since these patients require urgent reperfusion therapy. Both European and American cardiology guidelines recommend implementation of a 12-lead electrocardiogram (ECG) within 10 min of arrival in the ED^{3,4}.

In contrast, in the absence of electrocardiographic changes consistent with ischemia, the ACS rate is low (1–8% depending on the number of risk factors)³, and ACS are associated with lower in-hospital mortality ^{4,5,6}.

Emergency Department (ED) triage systems for acute chest pain are either based on clinical features or on a 12-lead ECG. A recent study showed the systems having a similar diagnostic performance but different characteristics since clinical-based triage had a higher sensitivity and ECG-based triage had a higher specificity⁷. The lack of sensitivity of ECG based triage was explained by the fact that patients with a normal or non-ischemic ECG were assigned to a low-acuity triage score, defined as inadequate (false negative) for ACS patients. Conversely, the lack of specificity of clinical based triage was due to a large number of patients with benign pathology assigned to a high-acuity triage score to perform a 12-lead ECG within the 10 minutes after the first medical contact as required.

We therefore hypothesized that combination of 12-lead ECG and cardiovascular risk factor could increase the sensitivity of ECG based triage for chest pain patients with a normal or non-ischemic ECG.

Methods

Selection of participants

All consecutive patients above 18 years of age, presenting at ED with acute non-traumatic chest pain as main complaint will be systematically included in the study.

Study design

We plan a prospective, single-center, observational study in a teaching hospital in Brussels, Belgium.

Triage of chest pain patients will be performed using the "French Emergency Nurses Classification version 2" (FRENCH) triage system⁸, which is currently used in our ED. FRENCH score is a 5-levels triage system classifying patients from category 1 corresponding to the "immediately life-threatening condition" to category 5 corresponding to the "less or non-urgent situations". Maximum authorized waiting period before first medical assessment according to severity category are respectively: immediate response, 20 minutes, 60 minutes, 120 minutes and undefined. Initial triage of chest pain

patients is based on vital signs, than if normal patients with a normal or unmodified ECG are sorted into category 3, those with an abnormal ECG without evidence of ischemia are classified into category 2, while those with ECG showing signs of ischemia (ST elevation, ST depression, new onset of a left bundle branch block, or T-wave inversions) are classified into category 1. Patients with lateral chest pain of a probable musculoskeletal nature are sorted into category 4 without performing an ECG.

The FRENCH triage (ECG-based triage) will be compared to a modified FRENCH triage system (ECG Score- based triage) upgrading high-risk patients with a normal ECG from category 3 to category 2. We defined high-risk patients as patients having a Systemic Coronary Risk Estimation (SCORE) above 10 % according with the 2016 European Guidelines on cardiovascular disease prevention in clinical practice⁹. To facilitate calculation of the SCORE at triage, we defined one major or four minor criteria required to upgrade the patients.

The major criteria are:

- 1. History of Cardio-vascular disease
 - a. acute coronary syndrome
 - b. stroke or IAT.
 - c. aterial revascularization procedure of peripheral artery.
- 2. Diabetes
- 3. End-stage renal disease or dialysis

The minor criteria are:

- 1. Man
- 2. Above 60 years of age
- 3. Hypertension
- 4. Smoker
- 5. Dyslipidemia

The above criteria will be collected by the triage nurse using a computerized form designed for the study. On this basis, the computer will additionally sort the patients using our modified triage scale, with blinded result avoiding bias in the initial nurse triage. This modified triage will therefore not be taken into account and management of the patients will not be modified.

Medical data will also be collected by physicians using a dedicated computerized form, particularly cardiovascular risks factors and complications occurring during the ED stay (arrhythmia, heart failure, shock).

The final diagnosis will be determined at the end of a 30-day follow-up, by either reviewing patient's files or a phone call to patients or relatives. ECG interpretation and diagnosis of acute myocardial infarction will be based on the universal definition of myocardial infarction¹⁰. Pulmonary embolism and aortic dissection will be substantiated by computed tomography (CT), chest infection by relevant positive biomarkers and a chest X-ray, gastroesophageal reflux by gastroscopy or positive therapeutic test with a proton pump inhibitor, and abdominal pathology by biology, imaging, or both.

Musculoskeletal pain will be diagnosed if all of the above-mentioned investigations are normal, and movement and palpation enhanced superficial pain. Finally, patients with a normal physical

examination, ECG, chest X-ray, and blood tests who did not report any event during the 30-day follow-up, and who therefore have no definite cause for their chest pain, will be sorted into a dedicated group called 'unclear diagnosis'.

The local hospital ethics committee approved the study protocol (CEHF 2017/18AOU/407), and patients will provide their written informed consent to participate in this study.

Statistical methods

To evaluate triage system's diagnostic performance, we will compare the triage score of patients with ACS (final diagnosis of STEMI, non-ST-elevation myocardial infarction [NSTEMI] or unstable angina [UA]) to a control group made up of patients with chest pain from mild severity diseases (including digestive diseases, chronic obstructive pulmonary disease (COPD) exacerbation, musculoskeletal chest pain, and all unclear diagnoses without any medical event in the follow-up period). Patients with other severe diseases, abnormal heart rate, abnormal blood pressure, respiratory distress, or hypoxemia will be excluded from the control group having a triage score driven by these conditions rather than by the ECG.

Since for ACS most of the arrhythmic events occur within 12 h of symptom onset^{11,12} and ACS patients should be monitored¹³, we defined for ACS a triage Score of 1 or 2 (high-acuity triage score) as adequate (true positive), and a triage Score of 3, 4, or 5 (low-acuity triage score) as inadequate (false negative). Conversely, for the control group with mild severity diseases, we defined a triage Score of 1 or 2 (high-acuity triage score) as inadequate (false positive), and a triage Score of 3, 4 or 5 (low-acuity triage score) as adequate (true negative). Receiver operating characteristic (ROC) curves will be generated to assess each triage system's accuracy in classifying a patient in ACS versus control group.

Capability of triage nurses to collect cardiovascular risk factors will be assessed comparing data collected at triage to these collected by the physician in the medical computerized file.

Sample Size

Based on our previous study (7), FRENCH score AUC under the ROC curve was 0.69. We hypothesized a correlation of 0.9 between the two tests. To show a difference of 0.06 between the AUC of the tests with a power of 0.8 (alpha 0.05) we calculated a sampled size of 233 patients. Given the uncertainty of the correlation, we planned to enrol 500 patients.

References

1

and non–Q wave myocardial infarction: results of the TIMI III Registry ECG Ancillary Study. J Am Coll Cardiol 30:133–140

insights from PARAGON-A applied to GUSTO-IIb1. J Am Coll Cardiol 38:64-71

- ⁶ Barrabe's JA, Figueras J, Moure C et al (2000) Prognostic significance of ST segment depression in lateral leads I, aVL, V5 and V6 on the admission electrocardiogram in patients with a first acute myocardial infarction without ST segment elevation. JACC 35(7):1813–1819
- ⁷ [name], Diego Castanares-Zapatero, Patrick Vanden Berghe, Philippe Meert, Alessandro Manara1 (2016) Comparison of clinical-based and ECG-based triage of acute chest pain in the Emergency Department. Intern Emerg Med DOI 10.1007/s11739-016-1558-8
- ⁸ Taboulet P, Moreira V, Haas L et al (2009) Triage with the French emergency nurses classification in hospital scale: reliability

and validity. Eur J Emerg Med 16(2):61-67

- ⁹ Massimo F. Piepoli (Italy), ArnoW. Hoes and all. 2016 European Guidelines on cardiovascular disease prevention in clinical practice. *European Heart Journal*, Volume 37, Issue 29, 1 August 2016, Pages 2315–2381

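### Category 4 patients get no triage ECG and score the same under both systems, yet they stay in the comparison while other controls with non-ECG scores are removed; this dilutes the reported specificity loss

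*Combined protocol and SAP*

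**What the plan says.** Study design (combined protocol and SAP) sets the category from vital signs first and then, if these are normal, from the ECG. One group bypasses the ECG: "Patients with lateral chest pain of a probable musculoskeletal nature are sorted into category 4 without performing an ECG". The modified system differs from FRENCH in one respect, "upgrading high-risk patients with a normal ECG from category 3 to category 2".

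Statistical methods then defines the outcomes. For controls it counts "a triage Score of 3, 4 or 5 (low-acuity triage score) as adequate (true negative"). For ACS patients it counts "a triage Score of 3, 4, or 5 (low-acuity triage score) as inadequate (false negative"). The control group expressly includes "musculoskeletal chest pain, and all unclear diagnoses without any medical event in the follow-up period".

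The same section lists who leaves the control group: "Patients with other severe diseases, abnormal heart rate, abnormal blood pressure, respiratory distress, or hypoxemia". The reason is that they are to be "excluded from the control group having a triage score driven by these conditions rather than by the ECG". Category 4 is not on this list, and no analysis restricted to ECG-triaged patients is described.

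ROC curves are planned for each system. The text does not say whether they use the 1–2 versus 3–5 split or all five levels.

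**The concern.** The Background hypothesis is about patients whose ECG is normal or shows no ischaemia: adding risk factors should raise the sensitivity of ECG triage in them. The price is specificity, because some controls in category 3 become false positives. Category 4 controls cannot pay that price. They have no triage ECG and no route to an upgrade, so they are fixed true negatives in both systems.

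The plan's reason for dropping other controls, that something other than the ECG set their score, fits category 4 as well but is applied on one side only. Abnormal vital signs or severe disease would tend to give high-acuity scores, which are false positives in a control; these patients are removed. Category 4 controls are certain true negatives; these are kept. The resulting control group matches neither the whole triage system nor the ECG-triaged population. Both specificities are raised and the reported specificity cost is reduced, by an amount that depends on the case mix of one emergency department.

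**Working it through.** **Inputs.** The plan gives a FRENCH AUC of 0.69, a target AUC difference of 0.06, a sample size of 233 and an enrolment of 500 (Sample Size). It gives neither the category 4 share nor an expected specificity loss, so the values below are assumptions. The figure of 233 cannot be reproduced uniquely, because no ACS-to-control ratio is stated. With the Hanley–McNeil variance, correlation 0.9 and a two-sided test, the total is 278 at 15% ACS and 217 at 20%. So 233 is attainable at an ACS share a little below 20%, and this point does not turn on it.

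**Notation.** q = category 4 share of controls; p = category 4 share of ACS; L = specificity loss and G = sensitivity gain among ECG-triaged patients.

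**Specificity.** In each system, Sp(all) = (1 − q) × Sp(ECG-triaged) + q. Subtracting the two systems:

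reported loss = (1 − q) × L

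With q = 0.20 and L = 0.25: 0.80 × 0.25 = 0.20, so a 25-point loss is reported as 20 points. For q = 10–30% the loss shrinks by 10–30%, whatever L is.

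**Sensitivity.** By the same argument, reported gain = (1 − p) × G.

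**AUC, dichotomised score.** Here AUC = (Se + Sp)/2, so

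reported difference = [(1 − p)G − (1 − q)L]/2

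With p = 0 this exceeds the ECG-triaged difference by qL/2. For q = 0.20 and L = 0.25 that is 0.20 × 0.25/2 = 0.025. For q = 10–30% and L = 15–35 points it runs from 0.10 × 0.15/2 = 0.0075 to 0.30 × 0.35/2 = 0.0525. If the planned 0.06 refers to a dichotomised AUC, 0.025 is 0.025/0.06 = 42% of it.

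**AUC, 5-level score.** A category 4 control ranks below every ACS patient in categories 1–3 under both systems, so those pairs add nothing to the difference. With p = 0, reported difference = (1 − q) × the ECG-triaged difference; in general the factor is (1 − p)(1 − q). A true gain therefore shrinks.

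**Illustration** (all inputs assumed, p = 0). ECG-triaged ACS patients are 35/25/40% in categories 1/2/3 and controls 5/20/75%. The rule upgrades 60% of category 3 ACS patients and 30% of category 3 controls. Sensitivity rises from 0.60 to 0.84 (G = 0.24) and specificity falls from 0.75 to 0.525 (L = 0.225).

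| q | Reported specificity loss | AUC difference, dichotomised | AUC difference, 5-level |
|---|---|---|---|
| 0 | 0.225 | 0.0075 | 0.0409 |
| 20% | 0.180 | 0.0300 | 0.0327 |
| 40% | 0.135 | 0.0525 | 0.0245 |

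Check at q = 20%: 0.80 × 0.225 = 0.180; 0.0075 + 0.20 × 0.225/2 = 0.0300; 0.80 × 0.0409 = 0.0327. As q rises, the two AUC forms move in opposite directions.

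**The case against.** The strongest reply is that the study enrols consecutive chest-pain patients and compares two whole triage systems. Category 4 is an output of both, keeping it leaves the number of newly created false positives unchanged, and dilution is not bias for that target. This stands as a reason to keep the all-patient result. It is not a full answer, because the plan has already left the whole-system target by removing controls whose score the ECG did not set.

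A reader might infer that the plan contradicts itself. The text does not support that: the exclusions are a specific list, category 4 is not on it, and musculoskeletal pain is a named control diagnosis. What can be said is that the stated reason is applied selectively.

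A reader might also infer that category 4 inflates the AUC gain of the modified triage. That holds for the dichotomised score when category 4 ACS patients are ignored. With the 5-level score a true gain shrinks, and the plan does not say which is used.

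Finally, the final-diagnosis text under Study design says "Musculoskeletal pain will be diagnosed if all of the above-mentioned investigations are normal", and a reader might conclude that category 4 patients cannot meet this. But the missing ECG is stated for triage only; nothing says that none is done later.

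One further objection stands: restricting to ECG-triaged patients selects on the triage result and drops any category 4 ACS patients. The restricted result should therefore accompany the all-patient one, not replace it.

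**Conclusion.** The point holds as a matter of selective exclusion and dilution. It follows from the text alone that category 4 scores are identical in both systems, that category 4 controls are true negatives and category 4 ACS patients false negatives in each, and that the reported specificity loss is (1 − q) times the loss among ECG-triaged controls. The size is not known, because the documents do not give q; an assumed 10–30% means a loss smaller by 10–30%.

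The AUC difference also depends on q, but the direction is open: +qL/2 for the dichotomised score (ignoring category 4 ACS), or multiplication by (1 − q) for the 5-level score (with no ACS in category 4). The documents do not support a claim that the plan is biased towards the modified triage on AUC, or that the all-patient analysis is invalid.

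**What to change.** Keep the all-patient comparison. Beside it, pre-specify a comparison of sensitivity, specificity and AUC in patients whose category was set by the triage ECG, defined as categories 1–3 with normal vital signs. Apply this definition to ACS patients and controls alike: the present vital-sign exclusion covers controls only, so categories 1–3 alone would still include ACS patients triaged on abnormal vital signs. State whether the ROC uses the dichotomised or the 5-level score. Report the number of category 4 patients by final diagnosis, so that q and the count of category 4 ACS patients are visible.

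The cost is a few sentences in the analysis plan and one extra table, with no change to triage or patient care. The vital signs needed are those the plan already uses to exclude controls. The restricted analysis will have fewer patients, hence less precision, and its specificities will be somewhat lower than in the all-patient result.

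### 'Unclear diagnosis' controls need a normal ECG, the item that also sets the FRENCH category; this tends to raise absolute FRENCH specificity, by an amount the documents cannot fix

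*Combined protocol and SAP*

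**What the plan says.** The rules sit in two sections of the combined protocol and SAP.

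- **Final diagnosis (Methods, Study design).** The 'unclear diagnosis' group consists of patients with a normal physical "examination, ECG, chest X-ray, and blood tests who did not report any event during the 30-day follow-up" and no definite cause for their pain. On the reading of tracings: "ECG interpretation and diagnosis of acute myocardial infarction will be based on the universal definition of myocardial infarction". On another control diagnosis: "Musculoskeletal pain will be diagnosed if all of the above-mentioned investigations are normal", together with pain on movement and palpation.
- **Control group (Statistical methods).** The list of mild diseases opens with the word 'including'. It names digestive disease, COPD exacerbation, musculoskeletal pain and "all unclear diagnoses without any medical event in the follow-up period". Patients with abnormal vital signs are left out so that the ECG drives the score.
- **Triage rule (Study design).** With normal vital signs, an ECG that is normal or unmodified goes to category 3, "those with an abnormal ECG without evidence of ischemia are classified into category 2", and an ischaemic ECG goes to category 1. The modified scale works by "upgrading high-risk patients with a normal ECG from category 3 to category 2".
- **Scoring of controls (Statistical methods).** "we defined a triage Score of 1 or 2 (high-acuity triage score) as inadequate (false positive"; levels 3 to 5 are true negatives.
- **Planned comparison (Sample Size).** "To show a difference of 0.06 between the AUC of the tests".

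The plan does not say whether the ECG used for the final diagnosis is the triage reading or a later one. It does not say whether 'normal' means fully normal or only free of ischaemic change. It does not say where an event-free patient with no cause found and an abnormal ECG is placed.

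**The concern.** The ECG is the main component of the test under evaluation, and it also helps to decide who counts as a control. If the two readings agree, an 'unclear diagnosis' control cannot be a FRENCH false positive. The matching patient with an abnormal ECG, who would have been one, drops out of the denominator. Specificity in that subgroup is then 100% by construction.

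What is at stake is mainly absolute accuracy. The plan will produce a ROC curve for each system, and the Background describes higher specificity as the strength of ECG-based triage, which is the property this selection can flatter. The stated hypothesis concerns sensitivity, which depends on the ACS patients and not on the choice of controls. The AUC comparison uses the same controls for both systems, so most of the effect is shared.

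**Working it through.** The plan gives no specificity and no control mix, so there is no figure of its own to reproduce here; the sample size of 233 does not enter. All inputs below are assumed. The figures are scenarios, not estimates.

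**Inputs.** m = share of mild patients with no cause found (0.4 or 0.6). a = share with a category 2 ECG (0.15, 0.25 or 0.35), taken as equal in patients with and without a cause. r = share of no-cause category 2 patients whose final ECG also reads abnormal, so that they drop out. b = share of mild patients whose ECG is abnormal but unmodified (category 3). s = share of no-cause patients in that group who drop out. u = share upgraded by the modified scale (0.2).

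**False-positive rate.** With no ECG selection it is a. As written it is

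f = a(1 − m·r) / (1 − m·a·r − m·b·s)

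and specificity inflation is a − f.

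**Step 1: without the offset (b = 0).** At a single cut, AUC = (sensitivity + specificity)/2, so AUC inflation is (a − f)/2.

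| r | FRENCH specificity inflation | FRENCH AUC inflation |
|---|---|---|
| 0 | 0 | 0 |
| 0.25 | 0.013 to 0.036 | 0.006 to 0.018 |
| 0.5 | 0.026 to 0.076 | 0.013 to 0.038 |
| 1 | 0.054 to 0.173 | 0.027 to 0.086 |

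As counts, take 200 mild patients, m = 0.6, a = 0.25, so 50 in category 2. With no selection, specificity is 150/200 = 0.75. At r = 0.5, 15 drop out: 150/185 = 0.81. At r = 1, 30 drop out: 150/170 = 0.88 (f = 20/170 = 0.118; the excess over the denominator's true rate is 0.25 − 0.118 = 0.132).

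If the category 2 share differs by group, the r = 1 range moves: 0.047 to 0.076 with 15% among no-cause and 35% among cause-found patients, and 0.125 to 0.194 the other way round.

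**Step 2: with unmodified abnormal ECGs (m = 0.6, a = 0.25, s = 1).**

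- r = 1, b = 0.1: f = 0.10/0.79 = 0.127; inflation 0.123.
- r = 1, b = 0.3: f = 0.10/0.67 = 0.149; inflation 0.101. The comparator without the offset is 0.25 − 0.10/0.85 = 0.132.
- r = 0.25, b = 0.1: f = 0.2125/0.9025 = 0.235; inflation +0.015.
- r = 0.25, b = 0.2: f = 0.2125/0.8425 = 0.252; inflation −0.002.
- r = 0.25, b = 0.3: f = 0.2125/0.7825 = 0.272; inflation −0.022.

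Rearranging, a − f is positive exactly when r(1 − a) > b·s. With equal agreement in both groups (r = s > 0) this becomes 1 − a > b, which holds whenever some patients have a fully normal ECG. The bias then stays upward but is smaller. It can vanish or reverse only when agreement is low for category 2 ECGs and high for unmodified ones.

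**Step 3: if 'normal' means only no ischaemic change.** Category 2 patients stay and only no-cause category 1 patients drop out. With share c of mild patients in category 1, inflation = (c + a) − (c + a − m·c)/(1 − m·c). For c = 0.02 to 0.05 this gives 0.005 to 0.025.

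**Step 4: bias in the AUC difference.** At the single cut it is minus half the change in the proportion of controls upgraded.

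- Without the offset it is −u(a − f)/2: 0 at r = 0; −0.001 to −0.004 at r = 0.25; −0.003 to −0.008 at r = 0.5; −0.005 to −0.017 at r = 1. It is proportional to u.
- Category 1 only: −0.0005 to −0.0025.
- With the offset (m = 0.6, a = 0.25, b = 0.2, r = 0.5, s = 1), the retained fraction is 1 − 0.075 − 0.12 = 0.805. If only strictly normal ECGs are upgraded, the upgraded share goes from 0.2 × 0.55 = 0.11 to 0.11/0.805 = 0.137, a bias of −0.013. If 60% of unmodified-ECG patients are upgraded as well, it goes from 0.11 + 0.12 = 0.23 to (0.11 + 0.048)/0.805 = 0.196, a bias of +0.017.

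**Limits.** This is a single-cut approximation, while the planned curve uses five levels. Musculoskeletal controls and category 4 patients without an ECG are not modelled.

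**The case against.** The strongest reply is that the exclusion is inferred. The control list is open-ended and may use 'unclear' loosely; if these patients are kept in practice, there is no bias. The only ECG standard the plan names is the universal definition of myocardial infarction, and if 'normal' means free of ischaemic change the effect is 0.5 to 2.5 points. Controls with a clean work-up are also a defensible choice, because they are less likely to hide missed ACS. The study is sized on an AUC difference, not on absolute specificity.

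Much of this stands. It limits the certainty and the size, and it makes the point one of clarification as much as of bias. It does not cancel an explicit normal-ECG criterion, and the plan does not adopt the reading under which the problem disappears. Left open, membership could be settled after the data are seen.

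The triage rule supplies a second valid objection. Unmodified ECGs are category 3, so the criterion removes true negatives as well as false positives. That is why Step 1 is an upper picture for its inputs.

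It also stands that the musculoskeletal definition does not name the ECG explicitly, and that probable musculoskeletal pain is triaged without one. Whether that group shares the problem is open.

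**Conclusion.** The plan, followed literally, selects one control subgroup on a component of the test being evaluated. This tends to raise absolute FRENCH specificity and AUC to the extent that final and triage ECG readings agree, with a partial offset from unmodified abnormal ECGs. The size cannot be computed from the documents. Under the main assumptions it runs from about 0 to 17 points before the offset, and from 0.5 to 2.5 points under the non-ischaemic reading. Sensitivity is unaffected.

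A reader might infer two stronger conclusions, and the documents support neither.

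- **That FRENCH specificity is certainly inflated, and substantially.** Agreement between readings, the share of unmodified ECGs and the fate of the abnormal-ECG patients are all unstated. At low agreement for category 2 ECGs the bias can be nil or slightly negative.
- **That the comparison is safe because any bias works against the modified scale.** That holds only if strictly normal ECGs alone are upgraded. If high-risk patients with unmodified ECGs are upgraded too, the bias can favour the modified scale. The bias is small against 0.06 in most scenarios, but the extremes with 20% of strictly normal ECGs upgraded reach about 0.017 either way (0.017/0.06 = 0.28), so no assurance on direction should be given.

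Severity is minor to moderate: a cheap improvement.

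**What to change.** For the accuracy analysis, define no-cause controls as patients with no ACS by final diagnosis, no other cause found and no event at 30 days, whether the ECG is normal, unmodified or abnormal. Count those triaged to level 1 or 2 as false positives. If the investigations required for a musculoskeletal diagnosis are meant to include the ECG, do the same there.

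Report the as-written normal-ECG definition as a sensitivity analysis. State which ECG reading counts, whether 'normal' means fully normal or only free of ischaemic change, and whether 'normal' in the upgrade rule covers unmodified tracings.

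The cost is one or two reworded definitions and one extra analysis. Triage category, final diagnosis and 30-day follow-up are already planned, and no patient's care changes. The downsides are a possibly less favourable FRENCH specificity, a little more analysis work, and less certainty that controls with an abnormal ECG are free of ACS. The last applies especially to ischaemic ECGs, because the plan gives no criteria for unstable angina; the sensitivity analysis shows how much it matters.

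### A pre-specified rerun in infarction patients, with the 30-day diagnosis masked to triage results, would show cheaply whether the AUC gain extends beyond unstable angina

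*Combined protocol and SAP*

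**What the plan says.** **Cases.** Statistical methods pools three diagnoses: "final diagnosis of STEMI, non-ST-elevation myocardial infarction [NSTEMI] or unstable angina [UA"].

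**Reference diagnosis.** Under Study design, "The final diagnosis will be determined at the end of a 30-day follow-up, by either reviewing" the file or telephoning the patient or relatives. The standard given for infarction is: "ECG interpretation and diagnosis of acute myocardial infarction will be based on the universal definition of myocardial infarction". Several non-coronary diagnoses also have stated tests. UA has none.

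**Controls.** The control group includes "all unclear diagnoses without any medical event in the follow-up period". The 'unclear diagnosis' group consists of patients with a normal "examination, ECG, chest X-ray, and blood tests who did not report any event during the 30-day follow-up".

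**Overlap of information.** The upgrade from category 3 to category 2 uses risk factors entered by the triage nurse. Physicians record the same kind of factors: "Medical data will also be collected by physicians using a dedicated computerized form, particularly cardiovascular risks factors". The plan also compares the two sources: "Capability of triage nurses to collect cardiovascular risk factors will be assessed comparing data collected at triage to these collected by the physician".

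**Masking.** The only masking stated concerns the computer's modified category, "with blinded result avoiding bias in the initial nurse triage", and that category plays no part in patient management. Nothing is said about what the person assigning the 30-day diagnosis may see.

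**Analyses.** One ROC comparison of ACS against controls is planned. There is no analysis by type of ACS and no sensitivity analysis.

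**The concern.** The two scales give different categories only to upgraded patients, who have a normal triage ECG and a high-risk profile. Any AUC gain must come from them. Among the ACS diagnoses, UA is the one for which the plan states no criterion.

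Suppose the risk profile in the file tips an upgraded patient from control to UA. For the modified scale, a false positive becomes a true positive. For FRENCH, a true negative becomes a false negative. Both changes favour the modified scale.

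As planned, a reader would see one pooled AUC difference. The reader could not tell whether the gain also holds for infarction, the part of ACS with a stated definition, or comes mainly from UA.

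**Working it through.** **The plan's own figure.** Sample Size gives 233 patients for AUC 0.69 against 0.75, correlation 0.9, power 0.8 and alpha 0.05. The ACS-to-control split and the sidedness are not stated, so 233 can be neither confirmed nor refuted. Two-sided, with Hanley-McNeil variances, the total is 116 at one control per case and comes near 233 only with between four and five controls per case. The point does not depend on this figure.

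**1. Shift per relabelled patient**

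From the documents: 500 patients and a target difference of 0.06. Assumed: all 500 analysed, ACS 10%, 18% or 25%, 15% upgraded in both groups, and a two-level AUC cut between categories 2 and 3.

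A two-level AUC is (sensitivity + specificity)/2. With a of n1 cases and b of n0 controls upgraded, the difference is D = 0.5 × (a/n1 − b/n0), which starts at zero here. After k upgraded controls are relabelled as UA:

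D(k) = 0.5 × [(a + k)/(n1 + k) − (b − k)/(n0 − k)]

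| n1 / n0 | a / b | D(1) | k to reach 0.03 | k to reach 0.06 |
|---|---|---|---|---|
| 50 / 450 | 7.5 / 67.5 | 0.0093 | 4 | 8 |
| 90 / 410 | 13.5 / 61.5 | 0.0057 | 6 | 12 |
| 125 / 375 | 18.75 / 56.25 | 0.0045 | 7 | 15 |

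For example, with n1 = 90 and k = 12: 0.5 × (25.5/102 − 49.5/398) = 0.063.

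Statistical methods does not say that the ROC curve is two-level. With more levels (controls 5/15/60/20% in categories 1 to 4; 42.7% of cases in categories 1 and 2, split 70/30, the rest in 3, which gives AUC 0.69), the shift per patient is 0.0064, 0.0039 or 0.0031. Adding 0.06 then takes 11, 18 or 22 patients.

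If upgrading does harm at the start (5 of 90 cases, 55 of 410 controls), D = −0.039, and after three relabelled patients it is still −0.021.

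**2. What the rerun would show, with and without mislabelling** (two-level AUC)

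- *Mislabelling:* n1 = 90, k = 12. The main analysis gives 0.063. Infarction only, with 15% of infarctions upgraded and UA left out of both groups, gives 0.5 × (0.15 − 49.5/398) = 0.013.
- *No mislabelling:* assume UA is 40% of ACS, and that 40% of UA, 15% of infarctions and 12% of controls are truly upgraded. The upgraded share of ACS is 0.4 × 0.40 + 0.6 × 0.15 = 0.25. The main analysis gives 0.5 × (0.25 − 0.12) = 0.065, and infarction only gives 0.5 × (0.15 − 0.12) = 0.015.

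The two pairs are almost the same, so the rerun cannot tell the two situations apart.

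**3. Precision**

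Assumed: 90 ACS, of whom 40% are UA, leaving 54 infarctions, and 410 controls. Hanley-McNeil variances v1 (AUC 0.69) and v2 (AUC 0.75); SE² = v1 + v2 − 2r√(v1·v2). Half-width = 1.96 × SE; power for 0.06 = Φ(0.06/SE − 1.96).

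| r | SE, 90 cases | half-width | SE, 54 cases | half-width | power, 54 cases |
|---|---|---|---|---|---|
| 0.9 | 0.0145 | 0.028 | 0.0183 | 0.036 | 0.91 |
| 0.8 | 0.0205 | 0.040 | 0.0259 | 0.051 | 0.64 |
| 0.7 | 0.0250 | 0.049 | 0.0316 | 0.062 | 0.47 |

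**The case against.** A reader might infer that UA labels will inflate the gain, or that a smaller infarction-only gain would expose biased labels. The documents support neither.

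- **A smaller gain can arise by design.** Study design puts an ECG showing ST elevation in category 1, so STEMI recognised at triage cannot be upgraded. Leaving UA out raises the STEMI share of cases and can shrink the gain without any labelling error. The Background hypothesis concerns patients with a normal or non-ischaemic ECG, so the restriction may also remove part of the target group. This stands, and it is the reason to add NSTEMI alone and the counts upgraded.
- **The route is narrow.** Patients whose examination, ECG, X-ray and blood tests are normal and who report no event become controls. What remains is upgraded patients with an abnormal test or a reported event, or a UA label assigned before that rule is applied; the plan does not say which takes precedence. In the two-level illustration, 0.06 requires relabelling 8 of 67.5, 12 of 61.5 or 15 of 56.25 upgraded controls (12%, 20% or 27%). Nothing in the documents suggests such rates.
- **Masking is partial.** Hiding the nurse form and triage levels leaves the risk factors in the medical file. This stands.
- **A written UA criterion is the more direct remedy for subjective labels.** That is fair, and stating one would help. It would not tell a reader whether the gain holds in infarction.

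UA is a legitimate part of ACS, and nothing here argues for removing it from the main analysis.

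**Conclusion.** A cheap improvement, not an error in the plan. The text supports three gaps: UA is pooled with infarction without a stated criterion; masking of the 30-day diagnosis to triage results is not described; and no analysis shows whether the gain holds in infarction. Influence of the risk profile on UA labels would favour the modified scale, but it is a possibility only.

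Its size cannot be computed from the documents, which give neither the UA share nor the proportion upgraded. On the assumed inputs, one relabelled patient moves the difference by 0.003 to 0.009, depending on the ACS share and the number of ROC levels. A few labels could not create the whole 0.06. These are shifts per patient, not a predicted result. The added analysis answers whether the gain extends to infarction, and nothing about why it might not.

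**What to change.** Keep ACS including UA as the main analysis. Add to the SAP:

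1. *As a sensitivity analysis, the paired AUC, sensitivity and specificity comparison will be repeated for STEMI plus NSTEMI, and for NSTEMI alone, against the same controls, with the remaining ACS patients left out of both groups. The number upgraded will be reported for STEMI, NSTEMI, UA and controls. Results are given as estimates with 95% confidence intervals and are not a success criterion.*
2. *STEMI recognised on the triage ECG is category 1 and cannot be upgraded, so a smaller gain after UA is left out is not in itself evidence of labelling bias; the analysis shows whether the gain extends to infarction.*
3. *The 30-day diagnosis will be assigned without sight of the nurse triage form, the FRENCH level or the modified level.*

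A useful clarification alongside: state the criterion used for UA and whether a UA label takes precedence over 'unclear diagnosis'.

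**Cost.** A few sentences, reruns on data already collected, and a small operational step to withhold the form and levels. Intervals widen, for example from a half-width of 0.028 to 0.036 at correlation 0.9 under the assumed fall from 90 to 54 cases, and further for NSTEMI alone. Any wrongly labelled patients would stay out of the controls, so a small part of their effect would remain in the rerun.
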